## **9.5 STUDY SIZE**

[figure not shown]
This study will identify covariates that represent potential confounding variables among dabigatran and warfarin users within a sampled population. The ability to identify a covariate and the precision for estimating potential confounding from the covariate will depend on the numbers of patients from whom electronic medical record data is extracted, and features of the covariate itself, such as how certain it is to be recorded in the medical record and whether binary (yes/no) or other.

The PS-matched dabigatran and warfarin initiators during Oct 2010– December 2013 period are approximately 20,000 each. Assuming that 5.5% of this study group will be linked to EMR, the EMR-linked subset up to Dec 2013 will consist of approximately 1100 patients in each exposure group.

The precision of estimated prevalence for a covariate obtained from the EMR depends on the prevalence of the covariate, and the sample size. With 10,000 dabigatran initiators, this study will estimate a patient characteristic that has a 10% prevalence with considerable precision (the 95% confidence interval will be 9.4% to 10.6%) ([Table 7](#)). A characteristic not captured in claims, but present in the medical record with a prevalence of 10% to 20% is plausibly a confounding variable and so this table enumerates characteristics with these prevalences. The table has not been extended below 10% since such lower prevalence characteristics have progressively less ability to produce meaningful confounding, so that while the study will have less precision to estimate such a characteristic, validation of the presence for such a low prevalence characteristic becomes unnecessary. At the other end of the range presented in the table, a characteristic with a prevalence above 20% will be identified with even greater precision, so that it also does not need to be depicted in the table.

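### Section 9.5 says precision improves above 20% prevalence; on Table 7's own scale it worsens between 20% and 80%, and two s.e. entries are ten times too small

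*Combined protocol and SAP*

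**What the plan says.** Section 9.5 bases the study size on the precision of a single prevalence: "The precision of estimated prevalence for a covariate obtained from the EMR depends on the prevalence of the covariate, and the sample size". Its worked example reads "With 10,000 dabigatran initiators, this study will estimate a patient characteristic that has a 10% prevalence with considerable precision", with a 95% interval of 9.4% to 10.6%, and it refers to Table 7. That table has a 95% CI column and a precision column labelled as the standard error, both in percentage points, for prevalences of 10% and 20% only.

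The section gives a reason for each end of that range. Below 10%, characteristics are said to have little ability to confound, so that "while the study will have less precision to estimate such a characteristic", checking them is treated as unnecessary. At the upper end, the section holds that "a characteristic with a prevalence above 20% will be identified with even greater precision", and on that ground it leaves such prevalences out of Table 7.

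For the linked subset the section projects that "the EMR-linked subset up to Dec 2013 will consist of approximately 1100 patients in each exposure group". The Abstract's study-size entry gives 15,000 matched initiators per group with the same 5.5% linkage.

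**The concern.** The binomial standard error, sqrt(p(1−p)/n), grows until p = 50%. The reason for leaving out the higher prevalences therefore runs against the metric in the table that it introduces, and it is the only reason given for stopping at 20%. The prevalences with the widest intervals at a given sample size are the ones not shown.

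This matters for Objective 1 (Section 9.7.1), which reports the prevalence of each EMR characteristic by exposure group to look for imbalance. Some Table 1 definitions are broad, such as any alcohol use, current and past smoking combined, or hyperlipidemia by note or LDL threshold. These could plausibly exceed 20%. The documents give no expected prevalences, so that is an assumption.

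**Working it through.** **Inputs.** Table 7: prevalences 10% and 20%, denominators 100 to 1,000,000, printed s.e. and 95% CI. Linked size per group: 20,000 × 0.055 = 1,100 (Section 9.5), and 15,000 × 0.055 = 825 (Abstract). Prevalences other than 10% and 20% are illustrative.

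**Step 1: reproduce the plan's figures.** Exact (Clopper-Pearson) intervals match all ten printed CIs. For example, 1,000/10,000 gives 9.4% to 10.6%, 10/100 gives 4.9% to 17.6%, and 200/1,000 gives 17.6% to 22.6%. With s.e. = sqrt(p(1−p)/n), eight of the ten printed standard errors match. The exceptions are the two 1,000,000 rows (step 5).

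**Step 2: the direction in Table 7 itself, from 10% to 20% prevalence.**

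| n | printed s.e. | printed CI width (points) |
|---|---|---|
| 100 | 3.0% to 4.0% | 12.7 to 16.5 |
| 1,000 | 0.9% to 1.3% | 3.8 to 5.0 |
| 10,000 | 0.3% to 0.4% | 1.2 to 1.6 |

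At 100,000 the printed values tie through rounding; unrounded, the s.e. is 0.095% against 0.126%.

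**Step 3: beyond the table, at the projected linked sizes.** The half-width is 1.96 × s.e.; s.e. and half-width are in points.

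| p | s.e., n=1,100 | half-width | s.e., n=825 | half-width | s.e./p, n=1,100 |
|---|---|---|---|---|---|
| 5% | 0.66 | 1.3 | 0.76 | 1.5 | 13.1% |
| 10% | 0.90 | 1.8 | 1.04 | 2.0 | 9.0% |
| 20% | 1.21 | 2.4 | 1.39 | 2.7 | 6.0% |
| 30% | 1.38 | 2.7 | 1.60 | 3.1 | 4.6% |
| 50% | 1.51 | 3.0 | 1.74 | 3.4 | 3.0% |
| 80% | 1.21 | 2.4 | 1.39 | 2.7 | 1.5% |
| 90% | 0.90 | 1.8 | 1.04 | 2.0 | 1.0% |

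The ratio of the s.e. at 50% to that at 20% is sqrt(0.25/0.16) = 1.25 at any n. Because p(1−p) is symmetric, the s.e. at 80% equals that at 20%, and above 80% it is smaller.

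**Step 4: below 10%.** The absolute s.e. at 5% (0.66) is smaller than at 10% (0.90), so that remark is also reversed on the table's scale. The last column shows that both remarks are right for s.e./p.

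**Step 5: the 1,000,000 rows.** sqrt(0.10 × 0.90/1,000,000) = 0.0003 = 0.03%, printed as 0.003%. sqrt(0.20 × 0.80/1,000,000) = 0.0004 = 0.04%, printed as 0.004%. The printed CIs agree with the larger values: an s.e. of 0.003% would give a half-width of 1.96 × 0.003 = 0.006 points and an interval printed as 10.0% to 10.0%, not 9.9% to 10.1%.

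**The case against.** The strongest defence is that the two directional remarks agree with each other. Less precision below 10% and more above 20% is how relative precision behaves, which suggests an unstated scale rather than a miscalculation. This may well be what was meant. It does not rescue the text, because Section 9.5 speaks of the precision of an estimated prevalence, gives intervals in percentage points and points to a column labelled as the standard error. A reader has no means of knowing that another scale applies.

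It can also be said that nothing depends on the sentence. The data already exist, the linked size follows from the matched cohort and the assumed linkage rate, and the visible text sets no precision target. That is correct, and it is why the severity is low.

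Several stronger readings are tempting but not supported:

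- A reader might infer that the statement is false for every prevalence above 20%. Above 80% it is true, and a definition as broad as Table 1's for hypertension history could fall there.
- A reader might infer that the sponsor is told that common characteristics need no check. The text says only that they need not appear in the table.
- A reader might quote the factor 1.67 between 10% and 50% (0.5/0.3). The table already covers 10% to 20%, so what it omits is the further factor of 1.25.
- A reader might call these the widest error bars in the study. That holds only among proportions at one sample size; eGFR, serum creatinine and the duration outcomes are not proportions.

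**Conclusion.** Wrong as written, low severity. On the scale that Table 7 uses, the upper-end remark is false between 20% and 80% prevalence and the lower-end remark is reversed. The worst case not shown is an s.e. 1.25 times that at 20%: at 1,100 per group the half-width grows by about 0.6 points, from 2.4 to 3.0, and at 825 per group it reaches about 3.4. These figures assume simple binomial sampling, a normal-approximation half-width and the plan's 5.5% linkage. How many outcomes fall between 20% and 80% cannot be determined from the documents.

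The two s.e. entries in the 1,000,000 rows are a separate, certain slip. They add no weight to the main point, since the study cannot reach that size.

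Nothing here shows that the study is too small or that any planned analysis is invalid.

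**What to change.** Correct both directional remarks together; changing only one would leave the section contradicting itself. Either state that absolute precision is poorest near 50% prevalence and improves towards 0% and 100%, or state that relative precision is meant and add s.e./p to Table 7.

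Give the worst-case 95% half-width at the projected linked size (about ±3.0 points at 1,100 per group, ±3.4 at 825), for example through a 50% row. Change the 1,000,000-row s.e. entries to 0.03% and 0.04%, or drop those rows.

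The cost is a few sentences and table cells in Section 9.5. The stated precision becomes slightly less favourable; sample size and analyses are unchanged.

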**Table 7 Precision of Estimates for Proportion Measures**

Numerator	Denominator	Prevalence	95% CI	Precision (s.e.)
10	100	10%	4.9%-17.6%	3.0%
100	1,000	10%	8.2%-12.0%	0.9%
1,000	10,000	10%	9.4%-10.6%	0.3%
10,000	100,000	10%	9.8%-10.2%	0.1%
100,000	1,000,000	10%	9.9%- 10.1%	0.003%
20	100	20%	12.7%-29.2%	4.0%
200	1,000	20%	17.6%-22.6%	1.3%
2,000	10,000	20%	19.2%-20.8%	0.4%
20,000	100,000	20%	19.8%-20.2%	0.1%
200,000	1,000,000	20%	19.9%- 20.1%	0.004%

**9.7 DATA ANALYSIS**

**9.7.1 Main analysis**

Representativeness of EMR

We will assess whether the subpopulation with linked EMR data is a representative sample of the full MarketScan cohort of oral anticoagulant medication initiators. In the full MarketScan cohort, the proportion of each exposure group with linked EMR data available will be determined. We will evaluate the claims-based covariates in the linked and non-linked subpopulations, separately by exposure group as well as overall, by examining prevalences

for categorical covariates and means and standard deviations for continuous covariates. These data will be summarized as in the example [Table 8](#) and will allow us to determine if there are any patient characteristics that are over-represented or under-represented in the EMR subpopulation. If EMR linkage is only available for a subset with considerably different characteristics than the full cohort or among a subset where the propensity score balance is not retained, then further remedies might be applied such as stratification or weighting.

**Table 8 Association between claims-based covariates and EMR linkage.**

Claims-based covariate	Dabigatran initiators		Warfarin initiators	
	N=		N=	
	Linked	Not linked	Linked	Not linked
Proportion (N)				
Age				
Age category 18-35				
Age category 36-64				
Age category 65-74				
Age category 75+				
Sex				
...				

*Objective 1: Descriptive*

The analyses for this objective will occur within the subpopulation of individuals with linked EMR data and will focus on describing the EMR-based clinical characteristics for the dabigatran and warfarin initiators. This table will provide an evaluation of the association between the EMR clinical characteristics and initiation of dabigatran or warfarin. [REDACTED]

The prevalence of each category for categorical characteristics and the mean and standard deviation for continuous characteristics will be calculated (as shown in the example [Table 9](#)). This analysis will aid in identifying EMR characteristics that are unbalanced across exposure groups and are therefore potential unmeasured confounders after PS matching.

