**Protocol for non-interventional studies based on existing data:**

Document Number:	c12696196-01
BI Study Number:	1160.219
BI Investigational Product(s):	PRADAXA (dabigatran)
Title:	Validation of predictors for oral anticoagulant medication choice using EMR data (Phase 3b of the BI/BWH Pradaxa study program)
Protocol version identifier:	1.0
Date of last version of protocol:	02 November 2016
PASS:	No
EU PAS register number:	Not available yet
Active substance:	Dabigatran etexilate
Medicinal product:	Pradaxa
Product reference:	EU/1/08/442/001-019
Procedure number:	EMEA/H/C/000829
Joint PASS:	Not applicable
Research question and objectives:	
The research question is whether select patient characteristics that may be incompletely captured by insurance claims data, differ between dabigatran and warfarin initiators.
 
Objectives:
 
 
1) Descriptive: To identify select clinical covariates from electronic medical records that might be associated with initiation of oral anticoagulant medications (dabigatran or warfarin) in NVAF patients at risk for stroke and are not usually well captured in the associated claims database
 
2) Prediction Rule: To assess how well EMR-based clinical characteristics can be captured on the basis of claims data only
 
3) Assess Balance: To assess the potential for unmeasured confounding in dabigatran vs warfarin comparative effectiveness and safety studies based on administrative claims
 

Proprietary confidential information © 2016 Boehringer Ingelheim International GmbH or one or more of its affiliated companies

	databases
Country(-ies) of study:	US
Author:	
Marketing authorisation holder(s):	Boehringer Ingelheim
MAH contact person:	
Date:	02 November 2016
Page 2 of 55	
Proprietary confidential information © 2016 Boehringer Ingelheim International GmbH or one or more of its affiliated companies. All rights reserved. This document may not - in full or in part - be passed on, reproduced, published or otherwise used without prior written permission	

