Variables:	
Patient characteristics derived from insurance claims (claims-based covariates)
 
This study will characterize patients initiating oral anticoagulant medications with respect to select characteristics, some of which might be reflected differently in claims data compared to electronic medical records prior to and including the date of initiation. These characteristics from EMR data are usually treated as covariates but will be considered outcomes in this validation study.
 
These characteristics include:
 
Primary Outcomes
 
 
• Obesity
 
• Smoking
 
• Alcohol consumption
 
• Abnormal renal function
 
• Bleeding history or predisposition
 
• Renal function (estimated GFR)
 
• Serum Creatinine
 
• Abnormal liver function
 
 
Secondary Outcomes
 
 
• Duration of atrial fibrillation
 
• History of adherence
 
• History/duration of hypertension
 
• Uncontrolled Hypertension (for HAS-BLED)
 
• History/duration of CHF
 
• Prior TIA
 
• Diabetes
 
• Hyperlipidemia
 
		

Name of company: Boehringer Ingelheim			
Name of finished medicinal product: Pradaxa® (Dabigatran etexilate), or warfarin			
Name of active ingredient: Dabigatran etexilate or warfarin			
Protocol date: 02 November 2016	Study number: 1160.219	Version/Revision: 1.0	Version/Revision date:
Variables:	
 
HAS-BLED Score
 
Use of antiplatelets or NSAIDs (needed for HAS-BLED)
 
		
Data sources:	This study will be conducted within MarketScan data linked to electronic medical records.		
Study size:	
Study cohort: approximately 15,000 dabigatran initiators PS-matched to 15,000 warfarin initiators
 
EMR-linked subset: approx. 5.5% of the study cohort.
		

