### 9.3 VARIABLES

#### 9.3.1 Exposures

The primary exposure is new initiation of warfarin or dabigatran. Initiators are defined as no anticoagulation with *any oral anticoagulant* in the 12 months before the index prescription. Comparison between these two groups of initiators will be made with respect to variables obtained from the EMR among patients who have been matched on the propensity score derived from insurance claims data.

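### The study asks whether two groups differ, but section 9.5 gives precision only for one group's prevalence, at about nine times the expected linked size, and the readable 9.7.1 names no interval for the contrast.

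*Combined protocol and SAP*

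**What the plan says.** The title-page table poses the research question as "whether select patient characteristics that may be incompletely captured by insurance claims data, differ between dabigatran and warfarin initiators". Section 9.3.1 repeats the target: "Comparison between these two groups of initiators will be made with respect to variables obtained from the EMR".

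Section 9.5 treats precision as a one-sample matter: "The precision of estimated prevalence for a covariate obtained from the EMR depends on the prevalence of the covariate, and the sample size". Its worked example is a 10% characteristic in 10,000 dabigatran initiators, with a 95% CI of 9.4% to 10.6%. Table 7 lists single proportions for denominators from 100 to 1,000,000.

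The same section expects far fewer patients with EMR data. It states "The PS-matched dabigatran and warfarin initiators during Oct 2010– December 2013 period are approximately 20,000 each" and then "Assuming that 5.5% of this study group will be linked to EMR", arriving at about 1,100 linked patients per group. The abstract applies the same linkage rate to a smaller cohort: "approximately 15,000 dabigatran initiators PS-matched to 15,000 warfarin initiators".

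In 9.7.1, Objective 1 calculates prevalences, or means and standard deviations, for each drug. The readable Table 9 shell has one column per drug. Its stated use is: "This analysis will aid in identifying EMR characteristics that are unbalanced across exposure groups and are therefore potential unmeasured confounders after PS matching". Objective 3 plans logistic regressions that predict drug choice from covariates, and the abstract says the strength of those associations will guide the confounding assessment.

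**The concern.** The quantity of interest is a contrast, and section 9.5 never says how well it will be estimated. A reader of 9.5 comes away with a half-width of about 0.6 points, a figure that belongs neither to a difference nor to the linked sample.

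The readable analysis text does not close the gap. Table 9 shows no difference, standardized difference or interval. Objective 3 names a model but no interval, and no guide to reading a null result. Section 9.11.2 has the data vendor evaluate balance of the EMR characteristics and points to 9.7 for the detail.

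Two errors become possible. Similar columns in a modest sample could be taken as evidence of balance when the data cannot exclude an imbalance of several points. Equally, a chance difference could be flagged as a confounder. The judgement carries forward, because Objective 2 concentrates on covariates found to represent potentially important unmeasured confounding.

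**Working it through.** **Inputs from the documents.** Matched cohort per group: 20,000 (9.5, to December 2013) or 15,000 (abstract, to December 2014). Linkage: 5.5%. Matching: 1:1 (9.11.1). Prevalences: 10% and 20% (9.5). The 50% prevalence is added here as the least favourable case.

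**Reproducing the plan's own figures.** The exact (Clopper-Pearson) 95% interval for 1,000/10,000 is 9.42% to 10.60%, which matches the text; the same method reproduces all ten intervals in Table 7. The linked size is 20,000 × 0.055 = 1,100, also as stated. The abstract's cohort gives 15,000 × 0.055 = 825.

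**One group at the linked size.** At 10% prevalence the exact interval is 8.3% to 11.9% with 1,100 patients and 8.0% to 12.2% with 825. At 20% it is 17.7% to 22.5% and 17.3% to 22.9%.

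**The difference.** With equal groups of n and common prevalence p, the 95% half-width is 1.96 × √(2p(1−p)/n). For p = 0.10 and n = 1,100: 1.96 × √(0.18/1,100) = 1.96 × 0.01279 = 0.0251.

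| Prevalence | 1,100 per group | 825 per group |
|---|---|---|
| 10% | ±2.5 points | ±2.9 points |
| 20% | ±3.3 points | ±3.9 points |
| 50% | ±4.2 points | ±4.8 points |

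Against the illustrated half-width of 0.59 points at 10%, the ratio at 1,100 per group is 2.51/0.59, or about 4. It has two sources: √2 for a difference, and √(10,000/1,100) = 3.0 for the sample size.

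**Standardized difference.** Near zero its standard error is about √(2/n): 0.0426 at 1,100 and 0.0492 at 825. The half-widths are ±0.084 and ±0.097.

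**Odds ratio.** For an unadjusted odds ratio at the null, the standard error of the log is √(2/(n p(1−p))). At 1,100 per group the 95% interval is about 0.76 to 1.32 at 10% prevalence and 0.81 to 1.23 at 20%. At 825 it is about 0.73 to 1.38 and 0.79 to 1.27.

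**Power, for scale.** The documents state no target difference. Taking a two-sided 5% test as an assumption, 1,100 per group gives 60% power for 10% versus 13% and 40% for 20% versus 23%. At 825 the figures are 48% and 32%.

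The groups are treated as unpaired because patients, not pairs, enter the linked subset (9.11.2). If linkage were independent within pairs, only about 5.5% of linked patients would have a linked partner.

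**The case against.** **A contrast is planned.** Objective 3 regresses drug choice on covariates, and the abstract uses the strength of association. Such models ordinarily yield odds ratios with standard errors. A reader might infer from Table 9 that imbalance will be judged only by comparing two columns; the documents do not support that. What stands is that the readable Objective 3 names no interval, and 9.5 gives no precision for its contrast either.

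**Redaction.** Text is blacked out directly after the Objective 1 sentence on association, and in a row and the note of Table 9. The contents page places 9.7.1 on pages 34 to 38, while the readable Objective 3 is one sentence. A contrast measure or threshold may exist unseen, so its absence is established for the readable text only. The prose of 9.5 and Table 7 carry no redaction mark that would explain their single-group focus.

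**How a null result is read.** A reader might infer that an absence of visible difference will be reported as balance. No passage says so. The supportable statement is that it could be, since no readable rule guards against it.

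**The ±0.10 benchmark.** One could calculate that a truly balanced characteristic has only a 30% chance (1,100 per group) or 6% (825) of a 95% CI inside ±0.10 on the standardized scale. That margin is not in the documents. Whether 0.10 matters depends on outcome associations, which 9.9 says this study does not assess. Those probabilities are illustrative and do not carry the conclusion.

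**Partial acknowledgement.** Section 9.5 says precision depends on the number with extracted EMR data, Table 7 has rows at 1,000, and 9.9 warns that dabigatran numbers could be small. This is fair, but none of it states the precision of a difference.

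**Conclusion.** The point holds in a limited form. Section 9.5 quantifies a quantity other than the one the study asks about, and its worked example uses a sample about nine times the expected linked size (10,000/1,100 = 9.1). For the contrast, the 95% half-width is about 2.5 to 4.2 points at 1,100 per group and 2.9 to 4.8 at 825, across prevalences of 10% to 50%. The readable Objectives 1 and 3 name no interval, so an inconclusive comparison could pass as balance, or a chance difference as confounding.

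The figures assume unpaired groups of equal size, a common prevalence, full ascertainment in the linked subset, and 5.5% linkage. Characteristics recorded for only part of the subset would be less precise. The documents do not show that the plan lacks a between-group analysis, or that it commits to reading null results as balance.

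**What to change.** 1. In 9.5, replace the 10,000-patient single-group illustration with the precision of the dabigatran-minus-warfarin difference at the projected linked size: about ±2.5, 3.3 and 4.2 points at 10%, 20% and 50% prevalence with 1,100 per group, or ±2.9, 3.9 and 4.8 with 825. Show both until the two cohort sizes are reconciled.
2. Add to every row of Table 9 the difference and the standardized difference, each with a 95% CI, using the mean difference for continuous characteristics. Report 95% CIs for the Objective 3 odds ratios. State that balance is interpreted from these intervals, not from the absence of a visible difference.

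A margin such as ±0.10 may be shown as an illustrative benchmark; a formal equivalence verdict on each row is not needed.

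The cost is a paragraph in 9.5, two columns in Table 9 and a sentence under Objective 3, with no new data. The downside is that the stated precision becomes less favourable and many rows will be visibly imprecise. If redacted text already supplies part of this, only the remainder is needed.
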